CKD-ND	Chronic kidney disease with subject not on dialysis
CMH	Cochran-Mantel-Haenszel
CRF	Case report form
CRP	C-reactive protein
CS	Clinically significant
CSE	Composite safety endpoint
CSP	Clinical study protocol
CSR	Clinical study report
DSMB	Data and safety monitoring board
ECG	Electrocardiogram
ECRF	Electronic case report form
EOS	End of study
EOT	End of treatment
EQ-5D-5L	EuroQol Health Utility Index, 5 dimensions 5 levels
ESA	Erythropoiesis-stimulating agent
FAS	Full Analysis Set
FDA	Food and Drug Administration
Hb	Hemoglobin
HDL	High-density lipoprotein
HR	Hazard ratio
HRQoL	Health Related Quality of Life

Abbreviation or special term	Explanation
ITT	Intention To Treat
IV	Intravenous
KM	Kaplan-Meier
LDL	Low-density lipoprotein
LTFU	Lost to follow up
MACE	Major Adverse Cardiovascular Event
MAP	Mean Arterial Pressure
MAR	Missing At Random
MCH	Mean Corpuscular Hemoglobin
MCHC	Mean Corpuscular Hemoglobin Concentration
MCMC	Markov Chain Monte Carlo
MCV	Mean Corpuscular Volume
MedDRA	Medical Dictionary for Regulatory Activities
MMRM	Mixed Model of Repeated Measures
MNAR	Missing Not At Random
N (or n)	Sample size
NCS	Not clinically significant
PCS	Potentially clinically significant
PEY	Patient-exposure-year
PMM	Pattern Mixture Model
PPS	Per-protocol set
PSAP	Pooled Statistical Analysis Plan
RBC	Red blood cell
SAE	Serious adverse event
SAP	Statistical Analysis Plan
TEAE	Treatment Emergent Adverse Event
TESAE	Treatment Emergent Serious Adverse Event
TIBC	Total iron binding capacity
TIW	Three times weekly
TSAT	Transferrin saturation
US	United States
VAS	Visual analogue scale

Abbreviation or special term	Explanation
WBC	White blood cell

SAP AMENDMENT HISTORY

Date	Brief description of change
28 September 2018	
The primary safety objective of this study is to contribute to the safety data in the pool safety analysis. Thus, analyses of CV safety will be conducted in accordance with the pooled safety analysis plan (PSAP).. These analyses will be made by study, as described in the PSAP, then pooled adopting meta-analysis techniques.
 
The primary efficacy endpoint has been specified as the primary efficacy endpoint for the FDA. The first secondary efficacy endpoint for the FDA has been specified as the primary endpoint for the EU health authorities.
 
Another change in this SAP is the ordering of the secondary efficacy endpoints to align with the order of the other phase 3 studies in the DD program.
 
The censoring criteria at a primary analysis censoring date has been omitted to align with the censoring rules in the PSAP.
 
A full list of the major changes are listed in Section 6.

25 January 2018	
The most important change in edition 3.0 is how the analysis of the primary safety composite endpoint MACE is conducted. There has been a strategic change in how to address CV safety in the project. No hypothesis testing, and no formal NI-margin for the safety endpoints will be adopted for this SAP. In alignment with the pooled SAP (PSAP) the focus will be on estimation and in providing a complete and transparent pattern of results for CV safety through the adoption of the “Totality of Evidence” approach. For full details regarding the ”Totality of Evidence” approach, please refer to the PSAP.
 
Other main changes are the addition of a primary efficacy endpoint, and addition of further secondary endpoints, as well as ordering of the secondary endpoints, done to harmonize with the other pivotal studies in this indication.
 
A comprehensive list of changes from the previous edition of the SAP is available in Section 6.

Date	Brief description of change
08 July 2016	Changes from SAP Edition 1.0: Following comments from the US Food and Drug Administration (FDA) on the CSP on March 13, 2015, it was decided that the analysis method for the first secondary endpoint regarding Hb change to be a multiple imputation ANCOVA. Furthermore, additional changes have been made to align with the CSP amendment, edition 6.0. For all major changes from SAP Edition 1.0, see Section 6.

1. STUDY DETAILS

1.1 Study objectives

This study is part of a study program for chronic kidney disease dialysis dependent (CKD-DD) subjects. The other phase 3 studies in the study program are the FibroGen FG-4592-063 and FG-4592-064 studies and the Astellas 1517-CL-613 study. There is a separate pooled statistical analysis plan (PSAP) for the statistical considerations concerning the overall program. The primary objective of this study is to evaluate the efficacy of roxadustat and to contribute CV safety data to the pooled safety analysis evaluating the safety of roxadustat for the treatment of anemia in CKD subjects on dialysis.

The objectives of the current study are to evaluate the safety and efficacy of roxadustat compared to epoetin alfa for the treatment of anemia in subjects receiving dialysis. Subjects on hemodialysis (HD) or peritoneal dialysis (PD) who have been treated with an erythropoietin analogue or have an indication for treatment with an erythropoietin analogue will be evaluated for eligibility and randomized at a 1:1 ratio to treatment with roxadustat (with discontinuation of prior erythropoietin analogue therapy) or to an active-control group treated with epoetin alfa. This study is also known as “ROCKIES”.

1.1.1 Primary efficacy objective

The primary efficacy objective is to evaluate the efficacy of roxadustat as compared to epoetin alfa based on Hb response during the study.

1.1.2 Primary safety objective

The primary safety objective is to contribute adjudicated CV safety data to pooled safety analyses across the phase 3 program per pooled SAP.

1.1.3 Secondary efficacy objectives

The secondary efficacy objectives are to evaluate:

- The efficacy of roxadustat as compared to epoetin alfa based on Hb response and level during the study.
- The efficacy of roxadustat based on Hb response in inflamed subjects.
- The effect of roxadustat on low-density lipoprotein (LDL) cholesterol as compared to epoetin alfa.
- The need for IV iron use in subjects treated with roxadustat as compared to epoetin alfa.
- The need for RBC transfusion as rescue therapy in subjects treated with roxadustat as compared to epoetin alfa.

1.1.4 Secondary safety objectives

The secondary safety objective is to evaluate the safety and tolerability of roxadustat as compared to epoetin alfa..

1.2 Study design

This is a Phase 3, multicenter, randomized, open-label, active-controlled study to evaluate the safety and efficacy of roxadustat compared to epoetin alfa for the treatment of anemia in dialysis subjects. Subjects on hemodialysis (HD) or peritoneal dialysis (PD) who have been treated with an erythropoietin analogue or have an indication for treatment with an erythropoietin analogue will be evaluated for eligibility and randomized at a 1:1 ratio to treatment with roxadustat (with discontinuation of prior erythropoietin analogue therapy) or to an active control group treated with epoetin alfa.

The study periods are as follows:

- **Screening Period:** Up to 6 weeks.
- **Treatment Period:** Subjects will be randomized (1:1) to open-label treatment with either roxadustat or epoetin alfa. Treatment duration is variable for individual subjects (estimated treatment up to 4 years). A common closeout will occur when the target number of MACE events has been accrued.
- **Post-Treatment Follow-Up Period:** 4 weeks from the end of treatment (EOT) visit to the end of study (EOS) visit. Subjects who discontinue study medication prematurely will be followed up for CV events, Hb measurements, vital status and hospitalizations until the end of the study (EOS), according to ITT principles, unless consent to participate is withdrawn.

1.2.1 Dosing

Roxadustat

Subjects currently treated with an erythropoietin analogue who are randomized to the roxadustat group will discontinue prior erythropoietin analogue therapy and initiate treatment with roxadustat at a starting dose according to Section 7 in the Clinical Study Protocol (CSP). Moreover, the dose is subsequently adjusted to achieve and maintain Hb levels between 10 and 12 g/dL. Subjects not currently treated with erythropoietin analogue will initiate roxadustat with dose selection based on body weight. Roxadustat will be administered orally three times a week (TIW) throughout the Treatment Period unless dose frequency reduction is required based on Hb levels.

Epoetin alfa

Initial dose selection of epoetin alfa for subjects treated with an erythropoietin analogue will be determined using a conversion table based on the subject's average prescribed

erythropoietin analogue dose during the preceding 4-8 weeks prior to enrollment in the study. Initial dosing of epoetin alfa for subjects not currently receiving an erythropoietin at study entry will be 50 IU/kg TIW with subsequent dose adjustments to achieve an Hb level of 11 g/dL and maintain an Hb level between 10 and 12 g/dL, consistent with approved prescribing information or the Summary of Product Characteristics for epoetin alfa.

[figure not shown]
Dosing for both treatment groups

Rescue therapy guidelines are provided to optimize standardization of the use of rescue therapy by investigators and to ensure safety of the individual study subjects. In the event of excessive erythropoiesis or excessive Hb levels equal or greater than 13 g/dL, the dose will be adjusted or put on hold at any time. Excessive erythropoiesis is defined as an Hb increase by >2.0 g/dL within a 4 week period.

1.2.2 Scheduled visits during treatment

During the treatment period, subjects will be contacted by telephone at week 1, and will attend study visits every two weeks from weeks 2 to 20. After week 20, study visits will occur every four weeks until the end of treatment period. A study end date will be defined based on when the planned number of events are estimated to be accrued; the EOT visit will occur as soon as possible after that date. An EOS visit will be performed 4 weeks after the EOT.

Figure 1 Study Flowchart

1.2.3 Stratification variables

The randomization in this study will be stratified by country. The stratification variables for the other studies in the program will be used in the analyses for this study as covariates, with addition of incident vs stable dialysis. The stratification variables are:

1. Baseline Hb (≤ 10.5 g/dL vs > 10.5 g/dL)
2. cardiovascular/cerebrovascular/thromboembolic medical history (Yes vs. No)
3. geographical region (US vs. Ex-US)
4. incident vs. stable dialysis (dialysis duration ≤ 4 months vs > 4 months from the randomization date)

Baseline Hb will be included in the analyses as a continuous covariate, hence, not as a dichotomous factor, unless specified otherwise. Throughout this document, the variable cardiovascular/cerebrovascular/thromboembolic medical history will be shortened as CV history, and the variable incident vs stable dialysis will be shortened as dialysis duration

CV history at baseline will be defined for subjects with history of any of the following diseases:

- Myocardial infarction
- Percutaneous coronary intervention
- Coronary artery bypass
- Cardiac failure congestive
- Ischaemic stroke
- Haemorrhagic stroke
- Cerebrovascular accident

1.3 Number of subjects

Primary efficacy variable: With at least 600 subjects, the study will provide at least 99% power to demonstrate non-inferiority of roxadustat versus epoetin alfa for the primary efficacy endpoint (i.e., Hb change from baseline to the average level during the evaluation period defined as Week 28 until Week 52). This assumes a difference (roxadustat minus epoetin alfa) of -0.30 g/dL, a non-inferiority margin for this difference of -0.75 g/dL and a standard deviation of 1.25 g/dL.

To contribute adjudicated CV events for the pooled CV analyses across the phase 3 program: approximately 2000 subjects will be randomized in a 1:1 ratio to either roxadustat or active control, i.e. epoetin alfa. The sample size for this study is driven by the overall requirement of adjudicated CV events for the phase 3 program in dialysis-treated CKD subjects (which consists of four studies in total targeting 611 subjects with MACE events). The three other studies in the study program are FG-4592-064, 1517-CL-0613, FG-4592-063.

2. ANALYSIS SETS

2.1 Definition of analysis sets

2.1.1 Intention To Treat Analysis Set (ITT)

All subjects who have been randomized to study treatment will be included irrespective of their protocol adherence and continued participation in the study. Subjects will be analyzed according to their randomized study medication irrespective of intake of study medication.

2.1.2 Per Protocol Set (PPS)

All randomized subjects without important protocol deviations and who have received at least 8 weeks of study treatment and who have valid corresponding Hb measurements will be included in the PPS. A valid corresponding Hb is defined as an Hb value from the central laboratory that is measured at least 2 weeks after the first dose and was either before the last study drug intake or at maximum three days after the last drug intake. Subjects will be analysed according to their randomized study medication irrespective of intake of study medication. Subjects with an important protocol deviation will be included in the PPS up to the time point when the violation was met. For criteria for PPS exclusion, see Table 1 in Section 2.2. Further details of important protocol deviations are available in a Protocol Deviation Plan. Subjects will be censored at the earliest of date of violating an important protocol deviation, the EOS visit, or at last intake of study drug.

2.1.3 Safety Analysis Set

All subjects who received at least one dose of randomized study drug will be included in the Safety Analysis Set. Throughout the safety results sections, erroneously treated subjects will be accounted for in the actual treatment group. If a subject has received both treatments, only the initial period will be utilized. Subjects will be censored at either, 7, 3 or 0 days after last intake of study drug. Consequently, there will be three versions of the Safety Analysis Set, and they will be referred to as On-treatment+7 (OT+7), OT+3 and OT+0 respectively.

2.1.4 Full Analysis Set (FAS)

The FAS consists of all patients in the ITT analysis set who received at least one dose of study drug and have baseline and at least one post-dose Hb assessment. If actual study medication received differs from the randomized treatment arm, the randomized treatment arm will be used for analysis for the FAS. This analysis set is primarily used for EX-US submissions.

2.1.5 Subjects who will not be included in any analysis sets

Subjects or sites identified prior to database lock (breaking of Sponsor blindness, open-label study) with major Good Clinical Practice violations and where the integrity of the data is strongly questioned through thorough independent investigations will be excluded from all analyses and all analysis sets. This includes but are not limited to subjects who have been identified to be part of a potential fraud investigation, subjects who have not signed an informed consent, subjects randomized in error (e.g. a subject considered to be a screen fail but by mistake randomized in the IWRS due to a technical error). Further, subjects being

randomized more than once will only contribute to the analysis one time. These patients will be analyzed according to their first assigned randomization number and treatment code. All AE's reported for the subjects will be assigned to the subject's first randomization number. All subjects excluded from all analysis sets will be properly documented.

2.2 Violations and deviations

The important protocol deviations are defined in [Table 1](#). Protocol deviations will be presented in a data listing.

Table 1 Criteria for Assessing Important Protocol Deviations

Number	Important Protocol Deviations	Level of Deviation ¹
1	Study drug compliance <75% where drug compliance is measured by comparing dispensed and returned drug (see Section 3.4).	Subject
2	Administration of wrong type of study drug (i.e. the one not randomized to) cumulatively more than 1 week	Visit
3	Administration of prohibited concomitant medication or non-drug therapy as defined in the protocol.	Visit
4	Administration of rescue therapy deviating from the protocol	Visit
6	Violation of inclusion or exclusion criteria. The key inclusion criteria are numbers 3-8. The key exclusion criteria are numbers 1-6, 9-16, 18 and 23. The full inclusion and exclusion criteria is available in the CSP.	Subject

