7. INVESTIGATIONAL PRODUCT AND OTHER TREATMENTS

7.1 Identity of investigational product(s)

Table 3 Identity of investigational product

Investigational product	Dosage form and strength	Manufacturer
Roxadustat	Oral tablets 20mg, 50mg and 100mg	FibroGen

The formulation number and batch number will be recorded in the study master file and identified in the clinical study report (CSR).

The only epoetin alfa to be used in the study is Procrit[®], Eprex[®] and Epogen[®], will be reimbursed in countries where this is possible, or otherwise centrally supplied by AstraZeneca.

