3. PRIMARY AND SECONDARY VARIABLES

3.1 Efficacy variables

3.1.1 Primary efficacy endpoint

US FDA: The primary efficacy endpoint for the US is the mean change from baseline in Hb averaged over week 28 to week 52. A multiple imputation approach with analysis of

¹ Subject-level deviations refer to important protocol deviations that will cause subjects to be excluded from the Per Protocol set, and therefore all their collected data from analyses based on this population.

Visit-level deviations refer to important protocol deviations that will cause only some data for subjects to be excluded from analyses based on the Per Protocol set, while the subjects remain in the Per Protocol set given that they did not meet any subject-level deviations. Data to be excluded from the Per Protocol analyses could be either data from a certain date, at which the deviation was met for the first time, onwards to the end of the study, or data during a period defined by the start and end dates of the deviation.

covariance (ANCOVA) will be applied as a method to handle missing data. Details of the multiple imputation ANCOVA are provided in Sections 4.2.4 and 4.2.5.

Hb results obtained from the central laboratory will be used for all Hb efficacy analyses. Baseline Hb is defined as the mean of the three last central laboratory Hb values from the screening and randomization visits.

Hb values under the influence of a rescue therapy will not be censored.

EU health authorities: The primary efficacy endpoint for the EU health authorities is the mean change from baseline in Hb averaged over week 28 to week 36, without having received rescue therapy within 6 weeks prior to and during this 8-week evaluation period.

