3.4 Treatment compliance

Subjects will be asked to return all unused study medication and empty packages to the clinic at each visit. The amount of dispensed and returned study medication will be recorded in the eCRF. The percentage treatment compliance will be calculated as:

$((\text{Overall amount of dose actually taken})/(\text{Overall amount of dose to be taken})) * 100\%$
Subjects taking $\geq 75\%$ and $\leq 125\%$ of planned study medication are considered to be compliant.

Compliance will be summarized as follows:

- Descriptive statistics will be summarized by the two treatment groups
- Percent compliance will be categorized according to the following three categories:
 - $< 50\%$ (significant drug non-compliance)
 - $\geq 50\%$, $< 75\%$, $> 125\%$ (moderate drug non-compliance)
 - $\geq 75\%$, $\leq 125\%$ (drug compliance)

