4.3.3 Primary efficacy endpoint analysis for EU (First Secondary endpoint for FDA)

Mean change in Hb from baseline to the subjects mean level from week 28 to week 36, without having received rescue therapy within 6 weeks prior to and during this 8-week evaluation period and will be analysed using MMRM. The model will contain terms for the baseline Hb measurement, treatment arm, visit, visit by treatment, CV history, geographic region and dialysis duration. Data up to visit of Week 52 will be included in the model.

Non-inferiority of roxadustat compared to epoetin alfa will be declared, and this test is successful, if the lower bound of the 2-sided 95% confidence interval of the difference between roxadustat and epoetin alfa exceeds -0.75 g/dL. The PPS will be used for non-inferiority. In addition to the comparison based on the PPS population, to address the formal test for non-inferiority, results will also be provided based on the FAS population, to allow also for a potential superiority comparison. The latter test is not part of the formal testing sequence.

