6.1 Changes of analysis from previous edition of the SAP

Table 4 Major changes of analysis from SAP Edition 3.0

SAP Section	Description of change	Rationale
1.1	The objectives of the study have been split to efficacy objectives and safety objectives.	For clarification.
1.1.4	A secondary objective to evaluate the efficacy of roxadustat based on Hb response in inflamed subjects has been added A secondary objective to evaluate the effect of roxadustat on LDL cholesterol has been added. The secondary objective of the effect on self-reported health status has been removed.	To harmonize with the secondary objectives of the other phase III studies in the program.
1.3	The description of the determination of the sample size related to CV safety has been shortened	Reference to a more detailed description of the requirements for sample size to address CV safety for this

		indication is made to the pooled statistical analysis plan.
2.1.1	FAS is renamed as ITT analysis set.	To align with the definition and terminology adopted in the other phase 3 trials in the study program.
2.1.2	An additional criteria to PPS has been added, which requires subjects to be on study drug for at least 8 weeks.	To align with the definitions adopted in the other phase 3 trials in the study program, and for clarification.
2.1.3	Added additional safety analysis sets; OT+7, OT+3 and OT+0. Removed OT+28.	To align with safety analysis sets in the PSAP.
	Full analysis set (FAS) is newly defined in a new section, Section 2.1.4.	To align with the definitions and terminology adopted in the other phase 3 trials in the study program, this analysis set will be required for the EU submission.
	Have added a subsection 2.1.5 that describes how subjects who will not be included in any analysis sets will be handled.	Not included in previous editions of the SAP.
2.2	Changed the level of deviation for the important protocol deviation of compliance to subject level from visit level.	To simplify the derivation of compliance and harmonize with the other phase III studies in the program
3	
The structure of this section and its subsections are rearranged.
 
The subsection on primary efficacy variables is split into two parts, one for US FDA and the other for EU health authority.
 
The subsections on primary and secondary safety variables is renamed as “Adjudicated CV events Analyses
	To harmonize with the primary variables of the other phase III studies in the program

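### Compliance for the per-protocol set has no stated time limit, so dosing after week 52 can decide who enters the EU week 28–36 non-inferiority test

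*SAP*

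**What the plan says.** SAP 2.2, Table 1, item 1 defines an important protocol deviation as "Study drug compliance <75% where drug compliance is measured by comparing dispensed and returned drug", assigns it to the subject level and refers to SAP 3.4. Footnote 1 to that table gives the consequence: "Subject-level deviations refer to important protocol deviations that will cause subjects to be excluded from the Per Protocol set", together with all their data.

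SAP 3.4 supplies the measure. The numerator is "Overall amount of dose actually taken" and the denominator is the corresponding overall amount due. No start or end week is given. The source is drug accountability: "The amount of dispensed and returned study medication will be recorded in the eCRF". Subjects taking 75% to 125% "of planned study medication are considered to be compliant".

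For the EU endpoint, SAP 4.3.3 says "The PPS will be used for non-inferiority". The model there takes data up to the week 52 visit. SAP 4.3.4 makes the same test the first FDA secondary endpoint. SAP 1.2 gives treatment as variable and up to about 4 years.

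Two other texts bear on the rule. SAP 2.1.2 and Protocol 8.3.2 keep a subject with an important deviation in the PPS until the deviation occurs. Protocol 7.1 says epoetin alfa "will be reimbursed in countries where this is possible, or otherwise centrally supplied by AstraZeneca".

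**The concern.** A per-protocol set should be built from adherence during the period that the endpoint reflects. Here the ratio has no stated end, the exclusion is all-or-nothing, and treatment can run for years after the last visit in the model. Doses missed in year 2 or 3 can therefore delete haemoglobin values from weeks 28–36. Good adherence later can likewise keep in a subject who took half the drug before and during the evaluation period. The set may drop subjects it should keep and keep subjects it should drop.

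What is at stake is the formal EU non-inferiority claim and entry to the FDA secondary sequence, in an open-label trial where selection after randomization matters most. The PPS repeats of the US primary and of the Hb-related secondary endpoints in SAP 4.3.6 inherit the same membership rule.

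**Working it through.** **Inputs from the documents.** Threshold 75%, subject level (SAP Table 1). Ratio of overall taken to overall due (SAP 3.4). Last modelled visit week 52 (SAP 4.3.3). Treatment up to 4 years, taken as 4 × 52 = 208 weeks (SAP 1.2). Sample size inputs from SAP 1.3: 600 subjects, 1:1, true difference −0.30, margin −0.75, SD 1.25 g/dL.

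**Assumptions.** Constant planned weekly dose; constant compliance within each stated period; T = 104, 156 or 208 weeks on treatment. The documents give no compliance distribution.

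**Step 1: the plan's own figure.** The standard error is 1.25 × √(2/300) = 0.102, and the distance to the margin is 0.75 − 0.30 = 0.45. Power = Φ(0.45/0.102 − 1.96) = 99.3%, which reproduces the stated 99% or more. That figure is for the US week 28–52 endpoint; none is given for the PPS test. On the same inputs, power is about 98% with 500 subjects and 95% with 400. Loss of numbers is therefore not the main issue; who is lost is.

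**Step 2: compliant early, less so later.** With 100% to week 36 and c afterwards, overall = [36 + c(T − 36)]/T. This falls below 75% when c < (0.75T − 36)/(T − 36). If compliance is 100% through week 52, replace 36 by 52.

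| T (weeks) | Excluded if c after week 36 is below | Overall at c = 65% after week 36 | Excluded if c after week 52 is below |
|---|---|---|---|
| 104 | 42/68 = 61.8% | 80.2/104 = 77.1% | 26/52 = 50.0% |
| 156 | 81/120 = 67.5% | 114/156 = 73.1% | 65/104 = 62.5% |
| 208 | 120/172 = 69.8% | 147.8/208 = 71.1% | 104/156 = 66.7% |

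At 208 weeks, 172/208 = 82.7% of the ratio comes from after week 36. A subject fully compliant through week 52, the last visit in the model, and 65% compliant afterwards scores (52 + 0.65 × 156)/208 = 73.8% and is also excluded.

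**Step 3: non-compliant early, better later.** With 50% to week 36 and 90% afterwards, overall = [18 + 0.9(T − 36)]/T: 76.2% at 104 weeks, 80.8% at 156 and 83.1% at 208. The subject is retained. With 80% afterwards the results are 69.6%, 73.1% and 74.8%, so the subject is excluded. Membership turns on later behaviour.

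**Step 4: the same subjects with a window ending at week 52.** 100% to week 36 and 65% afterwards gives (36 + 0.65 × 16)/52 = 89.2%: retained. 50% then 90% gives (18 + 0.9 × 16)/52 = 62.3%: excluded. A subject fully compliant to week 36 leaves only if compliance in weeks 36–52 is below (39 − 36)/16 = 18.75%.

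**Step 5: the two PPS rules.** SAP 2.1.2 and Protocol 8.3.2 retain data until the deviation date. Footnote 1 removes everything for a subject-level deviation. An overall ratio has no date on which it is first breached, so a programmer cannot apply both to this criterion.

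**Step 6: the two arms.** Protocol 7.2.1 describes dispensing of tablet bottles and of sponsor-supplied epoetin. No dispensed/returned count is described for reimbursed epoetin. Administered doses are recorded in the eCRF for all study drugs (Protocol 7.2.1 and 7.5).

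**The case against.** The strongest reply is that the whole-treatment window is an inference. SAP 3.4 says overall but names no period, SAP 2.1.2 has a rule limiting data by time, and details are left to a Protocol Deviation Plan that is not among the documents. This stands as a caution. It does not remove the problem: the plain reading of an overall ratio is the whole treatment period, and the time-limited rule cannot be applied to it.

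The subject-level choice was also deliberate. The change table in SAP 6.1 records "Changed the level of deviation for the important protocol deviation of compliance to subject level from visit level", to simplify the derivation and harmonise with the other phase 3 studies. That is a real reason, and a cost of changing it.

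The EU endpoint is also reported on the FAS, the US primary uses ITT, and OT+7 repeats are planned. These limit the consequences, but the FAS comparison is outside the formal sequence.

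Some stronger readings are tempting and not supported:
- A reader might infer that epoetin is given in the clinic and so cannot be counted. The current text does not say so; sponsor-supplied epoetin is dispensed, and Protocol 7.6 covers accountability for study drugs generally.
- A reader might infer that exclusions do differ by arm. That is possible, not shown.
- A reader might infer that Table 1 must also exclude above 125%. SAP 3.4 uses that range to classify and summarise compliance; excluding only under-dosing is a legitimate choice.
- A reader might want the window to end at week 36. The model uses data to week 52, so adherence in weeks 36–52 is relevant.

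**Conclusion.** The point holds, on the natural reading of SAP 3.4. A rule with no stated time limit decides membership of the set used for the formal EU week 28–36 test. With treatment of two to four years it can exclude subjects who were compliant through the analysed period and retain some who were not. It also cannot be reconciled with SAP 2.1.2 as written, and a comparable measure in both arms is not specified.

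The percentages above are illustrations that rest on constant planned dose and assumed compliance patterns. How many subjects would be affected is unknown. A reader might infer a bias of a particular size in favour of roxadustat, but the documents do not allow one to be estimated. They give no compliance rates, and no reason why a subject who lapses only after week 52 should have had a lower week 28–36 haemoglobin. Subjects who were non-compliant early would still be excluded under the correction. The matter deserves correction in the SAP; it does not touch the ITT-based US primary analysis.

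**What to change.** For PPS membership in the haemoglobin analyses:

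1. Compute compliance from first dose to week 52, the last visit in the model, or to last dose if earlier, and state this in SAP 3.4 and Table 1.
2. Derive it in both arms from administered versus planned doses in the eCRF, and name the source of the planned dose for epoetin, including reimbursed epoetin.
3. Reconcile SAP 2.1.2 (and Protocol 8.3.2) with footnote 1 for this criterion.
4. Report PPS exclusions by arm and reason.

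The cost is SAP wording, some derivation code and a small change in PPS membership. Administered doses are already collected. The main downside is a departure from the compliance derivation harmonised with the other phase 3 studies, which the SAP should acknowledge.
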